## 7. TRIAL PROCEDURES

This is a multi-centre, parallel randomized controlled trial study comparing the clinical outcomes of Monofocal Toric IOLs versus Monofocal non-Toric IOLs in cataract patients with astigmatism undergoing bilateral intraocular lens replacement surgery.

### 7.1 Recruitment

This study aims to recruit 140 participants over three years. The participants will be randomly assigned into Toric Monofocal IOLs group or non-Toric Monofocal IOLs group. The recruitment will take place at the cataract clinic at the REI of UHP. Adult cataract patients referred for cataract replacement surgery at REI, from community Optometrists and GPs, will enter a streamlined pathway whereby patients attend a single pre-surgical visit. During this clinic visit, the ophthalmologist surgeons will carry out medical screening and acquire relevant clinical measures, along with consent for the surgery.

The clinical team of REI will identify potential participants when they review the cataract surgery referral and medical records to arrange pre-surgery clinic appointment. A short version of PIS of this study will be sent out with the appointment letter to potential patients to give them time to read about the study before the recruitment at the clinic appointment.

The initial approach to recruit the potential participants will happen at the pre-surgery appointment at REI by the REI clinical team. One of the clinical team members will identify potential participants based

Vision and balance changes after bilateral implantation of Toric IOLs  
IRAS ID: 286913

on surgery referral forms or medical records, and approach the potential participants to ask if they would like to discuss about a research project or have read the short version PIS that was sent with the appointment letter. The patients will then be introduced to a member of the research team, present at the REI, to provide further explanation of the study and if willing, the potential participant will be consented. Consent will occur on the day at the clinic. The rationale for this is that potential participants only attend a single pre-surgical visit and so there are no other opportunities to bring a participant back to the hospital for consent prior to the surgery. Should a participant wish for a longer period to think about participating in the study, then consent will be taken at the first study visit. However, most participants will be consented at their routine pre-surgical clinical visit.

#### **7.1.1 Participant identification**

Cataract surgery is a streamlined service where all cataract patients referred for cataract replacement surgery are given a single pre-surgical clinical appointment at the REI of UHP. During this pre-surgical visit appointment, the clinical team will identify potential participants for the study based on the referral form. Adult cataract patients aged 50 years or above with astigmatism and have previously consented for routine bilateral cataract correction surgery at the NHS will be identified as potential participants for the study. The initial approach to the potential participants will be conducted by a member of the routine clinical care team, who will ask if the potential participants would like to be introduced to a member of the research team to discuss about a research study. If agreeable, then the potential participant will be introduced to the member of the research team present at REI. That team member will discuss the study with the potential participant, give them a copy of the PIS and will answer any questions about the study. If willing, the potential participant will then be consented. However, if the potential participant would like more time to consider their participation in the study, then their details will be collected, and they will be contacted at a later date. If they are willing to take part, consent will be secured at the first pre-surgical study visit at the UoP.

#### **7.1.2 Screening**

For potential participants who expressed interest in taking part in the study, they will be screened against inclusion and exclusion criteria by the Ophthalmologists (PI and his ophthalmology team) during the screening appointment based on routine pre-surgery examination result and medical record. No extra equipment or examination procedures will be needed.

Vision and balance changes after bilateral implantation of Toric IOLs  
IRAS ID: 286913

### 7.1.3 Payment

Any routine appointments for the cataract surgery procedure will not incur reimbursement.

The three additional assessment visits at the UoP, one before eye surgery (baseline), one 3-6 months after first eye surgery and one 3-6 months after second eye surgery will be reimbursed for a reasonable nominal fee (£20) to cover any travel expenses and the additional car parking fee.

### 7.2 Consent

Prior to participant recruitment and any procedures for this study, ethical approval will have been obtained from both the Health Research Authority and the NHS Research Ethics Committee.

Potential participants will be asked to sign the written informed consent form on the same day as their pre-surgical routine visit at the REI (where they are consented for surgery) by a member of the research team. This is to accommodate the cataract surgery clinical pathway and to reduce the need for the patients to travel back to REI for signing the written informed consent form. Following the current cataract surgery clinical pathway, patients attend the REI for a pre-assessment cataract clinic appointment to discuss cataract surgery with their ophthalmology surgeons. If the patients would like to go ahead, consent for surgery is obtained during this appointment. The patients are then placed on a waiting list and the next time they are seen is on the day of surgery. With discussion with the sponsor, it is felt that obtaining consent at REI, where the patients will be having their surgery, is most appropriate in terms of safety and it also allows potential participants to discuss elements of cataract surgery directly with the clinic team or the surgeons. If the consent is obtained at the study site, the academic researchers, who are not ophthalmologists, would not be able to discuss the surgical aspect related to this study. There is a long period between this pre-assessment appointment and the surgery (several weeks or months). So, the patients will have considerable time to further consider about their participation. At each study visit, time will be provided for participants to ask questions or reconsider their participation.

All potential participants will be informed that participation in this research study will be entirely voluntary. No one will be coerced against their will and no undue influence will be exerted upon the patient. The participants have the right to refuse participation without giving reasons and their decision will be respected. The participants are also free to withdraw at any time from the trial without giving

Vision and balance changes after bilateral implantation of Toric IOLs  
IRAS ID: 286913

reasons and without prejudicing his/her further treatment. Data collected up to the point of withdrawal from the study will be used in the analysis.

### **7.3 The randomisation schemes**

The PI will be responsible for recruitment of potential participants from the Cataract clinic at UHP and oversee the consent and eligibility process carried out by the study coordinator. All potential participants will be allocated a unique identification number. The CI, who is independent of the outcome assessments and interventions, will randomize the participants between the intervention and control groups. He will allocate a pseudonymous participant number from 1 to 140. Using simple randomisation with 1:1 allocation ratio through random.org, the 1 to 140 number will be randomly assigned into two groups (Toric IOLs versus non-Toric IOLs). The randomization list will then be passed to the PI, who when recruiting the participants at the pre-surgery clinic can know which type of IOLs (Toric or non-Toric) to prepare for the cataract surgery. At study commencement, each number will be allocated to one of the two groups randomly. This means that subjects are allocated to either arm of the study at the point of recruitment. The randomized list will be held by the PI, who delivers the intervention surgeries. The PI needs to know which lenses are allocated to the patients for surgery purposes but will not participate in the outcome assessment. The study coordinator who is the assessor of the outcome measures will be masked to the allocation of lenses.

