#### **7.3.1 Method of implementing the randomisation/allocation sequence**

The study randomization scheme will use simple randomization with a 1:1 allocation ratio using Microsoft Excel with same number of participants in each of Toric IOLs group and non-Toric IOLs group. The consenting patients will be randomly assigned to one of two groups: Toric IOLs with open loop haptic design and standard non-Toric IOLs of similar haptic design.

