### **7.4 Blinding**

The participants will be masked to the interventions prior to the surgery. They will be told which IOLs they received at the end of their final visit. The CI will conduct the simple randomization for the participants through the random.org and he will be masked to the outcome assessment. The randomized list of participants will be passed to the PI and his ophthalmologist team to prepare the IOLs and deliver the

Vision and balance changes after bilateral implantation of Toric IOLs  
IRAS ID: 286913

cataract correction surgery. So, the PI cannot be masked to the intervention, but he is masked to the outcome assessment.

The outcome assessors for study visits will be masked to the interventions given to the participants. In the post-surgery study visit, the outcome assessors will carry out the dynamic stability reassessment before any visual assessment to ensure they are still masked to the primary outcome measures as the visual assessment will reveal which types of the IOLs the participants received.

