### **10.2 Planned recruitment rate**

140 participants will be recruited over three-year period (minimal sample size of 110 plus 20% drop out rate estimation)

According to latest data from the National Ophthalmology audit database by the Royal College of Ophthalmologists, the REI of UHP performed 2525 cataract between 1st of September 2018 to 31st August 2019. The PI who performed cataract surgery at the REI reported around 3000 cataracts surgery were performed last year and the number is estimated to be similar this year. Due to COVID, there were longer waiting list and the waiting time between first and second cataract surgery at UHP has increased to about 4 months.

Approximately 40% patients undergo cataract surgery on both eyes (Jaycock, 2009 #281) (Day, 2015 #282). Among patients eligible for cataract surgery in NHS, 42% were reported to have mild to moderate astigmatism ( $>1.0$  D) (Day, 2019 #283). Therefore, it is estimated about 500 patients at REI annually will meet the inclusion criteria (needing cataract surgery in both eye with mild-moderate astigmatism) and our target for 140 participants out of the potential 1500 patients over three year

Vision and balance changes after bilateral implantation of Toric IOLs  
IRAS ID: 286913

should be a feasible number (10% of potential eligible patients), especially with the increasing number of cataract surgeries done every year.

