### 10.3.1 Summary of baseline data and flow of patients

[figure not shown]
Randomization	Sample size calculation with the G* Power 3 program N=140	Randomization list generated in MS Excel at the commencement of the study by the Chief investigator: independent of assessment and intervention	Execution- randomization list will be held by the PI (ophthalmologist at REI) so that they know who is allocated into either the intervention or control groups according to the list.
Outcome measures		Trial description	Outcome recorded
Primary outcomes Dynamic stability	1.Eye gazing characteristics	Gazing duration on obstacles during the obstacle negotiation.  Area of interest and corresponding glazing duration during stair walking	
 
Gazing duration and frequency on obstacles and area of interest.
 
Heat map on area of interest from eye tacking device
 
 
all data will be recorded and saved in file name in the format: participant number-obstacle-trial1/2/3-date.

	2.Movement biomechanics	
-participants perform Timed up and go (TU&G) test involving getting up from chair ,then walking over 3m level ground, turning and walking back to sit down on the chair
 
- participants walk over a 3m level ground with obstacles of different contrast colour to background.
 
- accelerometers of head tilting and change in movement of centre of gravity will be recorded during TU&G test and during crossing over obstacles.
	
 
accelerometers data of change in head tilting and centre of gravity will be recorded
 
Duration in seconds of TU&G test
 
 
all data will be recorded and saved in file name in the format: participant number-obstacle-trial1/2/3-date.

Secondary outcomes	1.Refraction and visual acuity	-standardized protocol for routine visual function test	-vision 20/20, sphere cylinder, axis -DVA, NVA -IOL rotation (for Toric IOL group only)
	2.Questionnaire	Short Fall Efficacy Scale International Fear of Falling Questionnaire CAT-PROM 5 Quality of life Questionnaire	

- A CRF form has been prepared for this study

Vision and balance changes after bilateral implantation of Toric IOLs  
IRAS ID: 286913

**Modified CONSORT flow diagram  
for**

**Vision and balance changes using after bilateral  
implantation of Toric versus non-Toric intraocular lenses in  

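### Allocation is not concealed: the full list, fixed at study start, is given to the principal investigator who recruits and screens

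*Combined protocol and SAP*

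**What the plan says.** **Sequence.** Section 7.3 says of the chief investigator (CI): "He will allocate a pseudonymous participant number from 1 to 140". It adds: "At study commencement, each number will be allocated to one of the two groups randomly". Section 10.3.1 also has the list generated at the start of the study.

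**Who receives it.** Section 7.3: "The randomization list will then be passed to the PI, who when recruiting the participants at the pre-surgery clinic can know" the lens type to prepare. Section 7.4: "The randomized list of participants will be passed to the PI and his ophthalmologist team". Section 10.3.1: "randomization list will be held by the PI (ophthalmologist at REI) so that they know who is allocated".

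**Who selects patients.** Section 7.3 makes the PI responsible for recruitment and for overseeing consent and eligibility, which the study coordinator carries out. Section 7.1.2 has interested patients "screened against inclusion and exclusion criteria by the Ophthalmologists (PI and his ophthalmology team").

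**Group sizes.** Section 7.3.1 calls the method simple randomisation, but "with same number of participants in each of Toric IOLs group and non-Toric IOLs group".

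**Assessor masking.** Section 7.4 acknowledges that the visual assessment gives away the lens type. Its procedural safeguard is to do the movement tests first within each post-surgery visit.

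**The concern.** Randomisation protects the comparison only if nobody who decides on entry can foresee the next allocation. Here the people who screen hold the list. A recruiter who knows the next lens can influence, without intending to, who is approached or how a borderline criterion is judged. Several exclusions in section 6.2 need judgement, such as the severity of blepharitis or the ability to understand the study. Section 7.9 also lets the PI, who knows the arm, withdraw a participant when eligibility is reassessed.

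Analysis cannot restore what is lost. The pre-surgery measurement in the mixed ANOVA deals with a baseline difference in the outcome itself, but not with differences in unmeasured prognosis.

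The masking point is secondary. An assessor who learned the lens type at visit 2 may still instruct and supervise the visit 3 movement trials.

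**Working it through.** **1. Is any allocation withheld until enrolment?** The passages closest to a safeguard are:

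| Section | What it says about timing | Does it hide the next arm from the list holder? |
|---|---|---|
| 7.3 | Allocation happens at recruitment | No |
| 7.3.1 | Consenting patients are assigned | No |
| 7.7 | Randomisation is described after study visit 1 | No |
| 13.7 | A study number is given on recruitment | No |
| Appendix 2 | Randomisation is marked at both screening and baseline | No |

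These say when a patient is numbered or allocated, and not consistently. None describes third-party release, sealed envelopes or a logged request. Section 7.5 adds a further conflict by saying that the CI holds the list.

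**2. How predictable is the next allocation?**
- Full list in hand, numbers issued in recruitment order (an assumption; section 7.3 gives no order): 140/140 = 100%.
- One-at-a-time release, truly simple randomisation: 70/140 = 50%.
- One-at-a-time release from a fixed list with m per arm, every past allocation remembered, always guessing the arm that is behind: expected correct guesses = m + (4^m / C(2m, m) − 1)/2. For m = 70, 4^70 / C(140, 70) = 1/0.0673 ≈ 14.86, which gives 70 + 13.86/2 = 76.93, and 76.93/140 = 54.9%.

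**3. Does simple randomisation fit equal arms?** The chance that truly simple allocation of 140 gives exactly 70:70 is C(140, 70)/2^140 = 6.7%. Section 7.3.1 therefore describes a fixed-total list, not simple randomisation.

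**4. How much room is there to select?** Section 10.2 gives about 3000 operations a year, 40% of patients with both eyes operated and 42% with astigmatism above 1.0 D.
- Reproducing its figure: 3000 × 0.40 × 0.42 = 504 a year, rounded there to 500, so 1500 over three years.
- The protocol's statement is "our target for 140 participants out of the potential 1500 patients over three year". 140/1500 = 9.3% (the protocol rounds to 10%), and 1500/140 = 10.7 potentially eligible patients per place.
- If the 3000 are operations and 40% of patients contribute two each (assumption): 3000/1.4 × 0.40 × 0.42 ≈ 360 a year, 1080 in three years, and 1080/140 = 7.7 per place.
- Both ratios are before the section 6.2 exclusions and refusals, so both are upper figures. They show opportunity and do not measure bias.

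**5. Sample size.** The stated 55 per group reproduces with a between-group F test, effect size 0.25, two measurements and correlation 0.5 (the last two assumed): N = 110, power 85.1%. Dropout gives 55/0.80 = 68.75, so 69 against the stated 70. Nothing in this point changes it.

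**6. Masking across visits.** Visit 2 is 3–6 months after first-eye surgery and visit 3 is 3–6 months after second-eye surgery. If the surgeries are G months apart, the gap between visits runs from (G + 3) − 6 = G − 3 to (G + 6) − 3 = G + 3 months.
- G = 4 (section 8.6): 1–7 months.
- G = 12 (one reading of the treatment duration in the trial summary): 9–15 months.

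Appendix 2 schedules vision and a lens-orientation item limited to the Toric arm at visit 2. The primary comparison in section 10.3.2 uses data collected after second-eye surgery. Appendix 1 gives movement tests to physiotherapists and eye drops to optometrists, but sections 4, 7.3 and 14.2 describe one coordinator as assessor, and 14.2 also as data manager. No rule keeps visit 2 vision results from the person running the visit 3 movement tests.

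**The case against.** The strongest reply has four parts.

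- **Foreknowledge is conditional.** The CI, not the PI, issues participant numbers, and the order is not stated. The trial flow chart and CONSORT diagram are not legible in the text reviewed and might show later release. This stands as a limit on the figure of 140 of 140. It does not supply a safeguard: concealment should not depend on an unstated order, and sections 7.3, 7.4 and 10.3.1 would still need correcting.
- **Others share the recruitment work.** The wider clinical team identifies patients from referrals, a research team member takes consent, and the masked coordinator carries out consent and eligibility. This reduces the risk. It does not remove it, because the PI oversees that process and section 7.1.2 gives screening to the PI's team, who hold the list.
- **The surgeon must know the lens.** True, but only for patients already enrolled and in time to order. That does not require sight of later allocations.
- **The masking gap is partly covered.** Section 7.4 requires masked assessors, the primary outcome is sensor-derived and averaged over three trials, and participants learn their lens only at the end of the final visit. This stands, which is why masking is treated here as a clarification only.

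**Conclusion.** The concern holds and must be fixed. As written, the plan fixes all allocations at the start and gives them to the people who recruit and screen, with no step that conceals upcoming arms. The number of upcoming allocations that could be named is 140 of 140 if numbers run in recruitment order, against 50% to 54.9% with one-at-a-time release. How much bias would follow cannot be derived from the documents. The rating rests on concealment alone; the masking gap across visits is secondary.

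**What to change.** **Section 7.3.** Delete the hand-over of the full list. Suggested replacement:

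> The allocation list is held by a named person who takes no part in recruitment, screening, surgery or study visits. Once consent and eligibility have been recorded and dated, that person issues the next participant number and sends the surgical team that participant's allocation only. Unreleased allocations are not available to anyone who recruits or screens.

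The sponsor's R&D office is one possible holder, if it has capacity; the documents do not say. Section 7.7 usually leaves 3–6 weeks to order a lens when consent is given at the clinic, and at least one week when it is given at study visit 1. Lens delivery time is not stated and should be checked for the second route.

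**Consistency.** Align sections 7.4, 7.5 and 10.3.1, naming in 7.5 whom to contact for emergency unmasking. State one time point for randomisation in section 7.7 and Appendix 2. Replace the term simple randomisation with wording that matches equal arms. Reconcile section 2.1, where the CI carries out pupil dilation at study visits, with section 4, where the CI has no part in outcome assessment.

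**Section 7.4.** State that whoever runs the movement tests neither performs nor sees a participant's visit 2 vision and lens-orientation results until that participant's visit 3 movement data are saved.

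**Cost.** Protocol wording, at most 140 release messages, and rostering of the optometrists and physiotherapists already named. Because section 14.2 makes the assessor the data manager too, someone else on the team would have to handle the visit 2 vision data until then. There is less slack for lens ordering when consent is given at study visit 1. No extra participants or equipment are needed.

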## 7.7 Trial assessments

Three study visits will be arranged for each participant who have given written informed consent to take part in the study.

**Study visit 1:** Pre-surgery baseline assessment will take place at the PAHC building of UoP, at least one week before the cataract surgery. After the participants have the cataract screening appointment at REI, they usually wait 3 to 6 weeks before the cataract surgery. The first study visit for the pre-operation baseline assessment will be arranged during this period. This also gives participants extra time to reconsider taking part in the study from when they signed the informed consent form at the REI. The study coordinator will reconfirm informed consent over the phone or by email (whichever is the preferred contact method) with the participant before arranging the first study visit and at the start of each study visit. If a participant needs to delay or cancel the cataract surgery due to a medical reason, the study coordinator will liaise with the PI who is the Ophthalmologist to confirm the participant is still suitable to take part in the study.

Intervention: participants will be randomized into two groups. One group will receive Toric Monofocal IOLs and the other group will receive standard non-Toric Monofocal IOLs.

**Study visit 2:** Reassessment of outcome measures will take place three to six months after first eye surgery at the PAHC building of UoP.

**Study visit 3:** Reassessment of outcome measures will take place three to six months after second eye surgery at the PAHC building of UoP.

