### 7.10 End of trial

The third study visit (3 to 6 months after the second eye cataract surgery) is the last contact with the participant. Upon completion of the last study visit for all 140 recruited participants (unless they have withdrawn) will be the end of the trial.

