## **10. STATISTICS AND DATA ANALYSIS**

### **10.1 Sample size calculation**

Sample size test calculation was carried out with the G\*Power 3.1 program (Faul *et al.*, 2007) for comparison of the main outcome measure of dynamic balance (between IOL design) using mixed ANOVA (repeated measures, between factor being the type of IOL).

Based on of the dynamic balance measurement (JERK score) in a previous study (Mancini *et al.*, 2011) an estimated medium effect size (0.25) will be used. With a power of 85% and level of significance ( $p$ ) set at 0.05 and effect size of 0.25, 55 participants will be required in each group (Monofocal vs Toric IOL). Accounting for a 20% drop out rate, 70 participants will therefore be recruited in each group (A total of 140 participants).

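### Section 7.3 fixes the arm at clinic recruitment, before the baseline visit, so people lost before that visit count as randomised without data; other sections time randomisation differently

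*Combined protocol and SAP*

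**What the plan says.** Section 7.3 gives the numbers 1 to 140 an arm when the study opens, passes the list to the PI for use while recruiting at the pre-surgery clinic, and concludes: "This means that subjects are allocated to either arm of the study at the point of recruitment". Section 7.1 places recruitment at the hospital's cataract clinic, which comes before study visit 1 at the university.

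The plan then leaves room for a change of mind. Section 7.7 has the coordinator reconfirm consent before visit 1 is arranged and again at the start of each visit, and says of the interval before visit 1: "This also gives participants extra time to reconsider taking part in the study from when they signed the informed consent form at the REI". Section 7.2 puts the gap from clinic to surgery at weeks or months; section 7.7 says it is usually 3 to 6 weeks. Patients who want longer to decide sign later: "If they are willing to take part, consent will be secured at the first pre-surgical study visit at the UoP" (section 7.1.1). Section 7.9 lets the PI or the coordinator withdraw someone found not to meet the criteria when eligibility is reassessed.

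Other sections give a different time for randomisation. Section 7.3.1 says it is consenting patients who are assigned. Section 7.7 puts "Intervention: participants will be randomized into two groups" between visit 1 and visit 2. Appendix 2 ticks randomisation at both Screening and Baseline.

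On numbers, section 7.10 closes the trial as follows: "Upon completion of the last study visit for all 140 recruited participants (unless they have withdrawn) will be the end of the trial". No section says whether a number vacated before surgery is reused or the person replaced.

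**The concern.** If the arm is attached at the clinic, everyone who changes their mind, is found ineligible or has surgery cancelled before visit 1 is already randomised. They have no baseline and no outcome, so they cannot enter the mixed ANOVA of sections 10.3 and 10.3.2, which compares pre-surgery with post-surgery values. Each takes one of a fixed 140 numbers. If the arm is drawn after visit 1, the same people are screening failures and cost the comparison nothing.

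The point does not depend on concealment; it would remain with a perfectly concealed list. At stake are the number analysed and whether the as-randomised set can be reported complete. There is also one opening for selective removal: the PI knows the arm and may withdraw people on reassessed eligibility after it has been fixed.

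**Working it through.** **Timing, side by side**

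| Place | When the arm is assigned |
|---|---|
| 7.3 | At recruitment, i.e. at the clinic, before visit 1 |
| 7.3.1 | Once the patient has consented; no visit named |
| 7.7 | Listed after visit 1, before visit 2 |
| Appendix 2 | Ticked at Screening and at Baseline |

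Sections 7.3 and 7.7 cannot both be followed for a patient recruited at the clinic. Appendix 2 can be read as serving two consent routes, because it also ticks informed consent in both columns.

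**The plan's sample size**

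Inputs from section 10.1: "With a power of 85% and level of significance" "set at 0.05 and effect size of 0.25, 55 participants will be required in each group". The test is a mixed ANOVA with lens type as the between-subjects factor. The number of repeated measures (m) and their correlation (ρ) are not given there. Section 10.3 describes pre- versus post-surgery, so I take m = 2, and I assume ρ = 0.5.

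- Noncentrality: λ = f² × N × m / (1 + (m − 1)ρ), with an F test on 1 and N − 2 degrees of freedom.
- N = 110: λ = 0.0625 × 110 × 2 / 1.5 = 9.17; power 0.851. The plan's 55 per group is reproduced.
- Sensitivity: for ρ from 0 to 0.8 the same test needs 74 to 132 in total with m = 2, and 50 to 128 with m = 3 (98 at ρ = 0.5).
- Drop-out: 55 / 0.8 = 68.75, so 69 per group. The plan's 70 is one more.

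**Margin in the 140**

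- Losses tolerated before completers fall below 110: 140 − 110 = 30, and 30/140 = 21.4%.
- After the planned 20%: 140 × 0.8 = 112.
- Further loss that can be absorbed: 1 − 110/112 = 1.8%.

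**Effect of loss before visit 1**

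The documents give no rate for it. There are two readings.

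1. The 20% already includes it: 112 completers against 110 needed, so no shortfall.
2. It comes on top, at an assumed rate q: completers = 140 × (1 − q) × 0.8.

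| q (assumed) | Completers | λ | Power (m = 2, ρ = 0.5) | Numbers to allocate for 110 completers, 110 / (0.8(1 − q)) |
|---|---|---|---|---|
| 0 | 112.0 | 9.33 | 0.857 | 138 |
| 5% | 106.4 | 8.87 | 0.839 | 145 |
| 10% | 100.8 | 8.40 | 0.819 | 153 |
| 15% | 95.2 | 7.93 | 0.796 | 162 |

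With m = 3 and ρ = 0.5, power at 5%, 10% and 15% would be 0.879, 0.861 and 0.841. The absolute figures therefore depend on inputs the plan does not state.

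If allocation follows visit 1, q drops out of the formula: 140 × 0.8 = 112 whatever is lost earlier.

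**The case against.** The case for leaving this as a small clarification is a fair one.

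- *The drop-out allowance.* Section 3.3 derives the 70 per group as the number to recruit in order to keep 55. If recruitment is at the clinic, loss from the clinic onward falls within the 20% and there is no shortfall. Section 13.3 also reports few dropouts in the team's previous lens trials. This stands: a shortfall is conditional and the loss rates above are assumptions.
- *Bias.* Participants are masked before surgery (7.4) and the coordinator is masked (7.3), so someone who changes their mind before treatment is not reacting to the arm. This stands for participant-led withdrawal. It does not cover the PI, who knows the arm and may withdraw people under 7.9; the documents give no sign that this would be done selectively.
- *Consent.* A reader might infer that some people are allocated before they sign, because 7.3 says "All potential participants will be allocated a unique identification number" and some patients sign only at visit 1. The documents do not support that. Section 7.3 introduces the 1 to 140 number separately, 7.3.1 confines assignment to consenting patients, and Appendix 2 pairs the consent and randomisation ticks.
- *Data.* A reader might also infer that everyone lost before surgery leaves nothing to analyse. That is true only of loss before visit 1. Someone lost between visit 1 and surgery has a baseline, which 7.2 keeps, although 10.6 discards the data of people withdrawn after missed visits.
- *Logistics.* The PI needs the arm in order to prepare the lens, lenses are ordered individually from pre-surgery measurements (8.4), and visit 1 may be as little as a week before surgery (7.7). This is a real constraint, but Appendix 2 does not tick lens dispensing until Baseline, so the schedule does not require an arm at the clinic.

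**Conclusion.** The point holds in limited form. The sections disagree on when the arm is assigned, and the rule in 7.3 turns avoidable losses before visit 1 into post-randomisation losses, drawn from a list that ends at 140 with no replacement rule. The main harm is lost numbers and an incomplete as-randomised set, without demonstrated bias.

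The size ranges from no shortfall, if the 20% runs from the clinic, to about 106, 101 or 95 completers and power of about 0.84, 0.82 or 0.80, if 5%, 10% or 15% are lost on top. Those rates are assumed, and the power figures rest on two measures and a correlation of 0.5. The change is worth making even if there is no shortfall, because it resolves the contradiction and protects the randomised set without raising the 140.

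**What to change.** Bring 7.3, 7.3.1, 7.7 and Appendix 2 to one rule, for example:

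*The CI assigns the next list number, and with it the arm, only after the participant has signed consent, been confirmed eligible and completed study visit 1. People who stop before then are screening failures, take no list number and do not count towards the 140.*

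Delete the sentence in 7.3 that allocates at recruitment, remove the Screening tick for randomisation in Appendix 2, and state in 3.3 and 10.1 that the 20% drop-out runs from randomisation. Because 7.3 currently hands the list to the PI, the new timing guards against removals by someone who knows the arm only if the PI learns each arm when the CI assigns it.

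The change does not reach losses between visit 1 and surgery. These remain post-randomisation losses within the 20%, and 7.2 and 10.6 should be reconciled on whether their data are kept.

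The cost is protocol wording and one practical constraint: lenses can be ordered only after visit 1, so visit 1 must be booked early enough in the pre-surgery wait for delivery. The documents give no delivery time, so the team should check this before adopting the rule.
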